#### **15.8.6.2 Supportive Analysis**

To assess the consistency of the primary analysis results, supportive analysis will be conducted using the PP population. Statistical methodology for the supportive analyses will be the same as that of the primary analysis, with the exception of the analysis population used. The PP population will be used for the supportive analysis while ITT population will be used for the primary analysis.

#### **15.8.6.3 Longitudinal Analysis**

Longitudinal data analyses will be conducted for selected endpoints; these will be pre-specified in the SAP.

### **15.8.7 Safety Assessments**

#### **15.8.7.1 Adverse Events**

All AEs will be presented by number of episodes and by number of subjects experiencing the event in each arm with information on time of occurrence and duration.

AEs (including ADEs) will be coded using the latest version of MedDRA. Treatment-emergent AEs (TEAEs) are defined as events with an onset on or after the first randomized treatment. TEAEs will be summarized by treatment arm, System Organ Class, and Preferred Term. The following TEAEs summaries will be provided:

- TEAEs by severity grade
- TEAEs by relationship to study treatment

In addition, separate summaries of SAEs (SADEs) and AEs (ADEs) resulting in discontinuation of study treatment will be presented.

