Weight gain	3 (7%)	9 (22%)	7 (17%)
Weight loss $< 5\%$	21 (50%)	13 (32%)	18 (43%)
Weight loss $\geq 5\%$	18 (43%)	19 (46%)	17 (40%)
Weight loss $\geq 10\%$	11 (26%)	5 (12%)	5 (12%)

The extent of weight loss at Day 87 was more pronounced in subjects on Gelesis100 2.25 g with impaired fasting glucose at baseline. The placebo-adjusted weight loss was 5.3% and the total body weight loss was 10.9% (Table 9). There was a significant negative correlation between fasting glucose at baseline and change in body weight at Day 87 in subjects on Gelesis100 2.25 g ( $r = -0.50$ ;  $P < 0.001$ ) contrasting with a lack of significant correlation in Gelesis100 3.75 g arm ( $r = -0.01$ ;  $P = 0.968$ ) and placebo arm ( $r = -0.06$ ;  $P = 0.708$ ).

**Table 9.** Body weight (% change from baseline) at Day 87 in the ITT population in subjects with impaired fasting glucose at baseline.

Arm	Number of subjects	Mean $\pm$ SD	P value (versus placebo)
Gelesis100 2.25 g	9	-10.9 $\pm$ 4.3	0.019
Gelesis100 3.75 g	9	-4.2 $\pm$ 5.7	0.348
Placebo	11	-5.6 $\pm$ 4.8	-

Treatment with Gelesis100 was safe and well tolerated. Thirty-one subjects (74%) on Gelesis100 2.25 g, 35 subjects (85%) on Gelesis100 3.75 g, and 36 subjects (84%) on placebo reported at least 1 AE during the study (mainly gastrointestinal AEs). Bloating, flatulence, abdominal pain, and diarrhea were the most common gastrointestinal AEs with lower prevalence in Gelesis100 2.25 g compared to placebo and Gelesis100 3.75 g

arms (Table 10). Common cold and headache were the most common non-gastrointestinal AEs. SAEs were observed in 3 subjects on placebo (gallstone and abdominal pain). The AEs were usually of mild intensity, occurred at different times during the course of the study, and resolved within 1 week in most cases.

**Table 10.** Gastrointestinal AEs\* in the safety population.

Parameter	Gelesis100 2.25 g (n = 42)	Gelesis100 3.75 g (n = 41)	Placebo (n = 43)
Any gastrointestinal AE	25 (60%)	31 (76%)	32 (74%)
Bloating**	12 (29%)	15 (37%)	16 (37%)
Flatulence**	11 (26%)	15 (37%)	13 (30%)
Abdominal pain**	9 (21%)	12 (29%)	15 (35%)
Diarrhea**	8 (19%)	10 (24%)	16 (37%)

\*Gastrointestinal AEs were solicited and recorded through a questionnaire. \*\*Similar AEs are grouped under one main term.

Dropout after randomization occurred in 2 subjects (5%) on Gelesis100 2.25 g, 10 subjects (24%) on Gelesis100 3.75 g, and 9 subjects (21%) on placebo. No AE was responsible for the dropout with Gelesis100 2.25 g.

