## **6.2 Secondary**

- To assess the decrease in serum insulin after repeated administration of Gelesis100 over a period of 168 days in overweight and obese subjects with and without type 2 diabetes
- To assess the decrease in insulin resistance (homeostasis model assessment-insulin resistance “HOMA-IR”) after repeated administration of Gelesis100 over a period of 168 days in overweight and obese subjects with and without type 2 diabetes
- To assess the decrease in plasma glucose after repeated administration of Gelesis100 over a period of 168 days in overweight and obese subjects with and without type 2 diabetes
- To assess the decrease in glycosylated hemoglobin (HbA1c) after repeated administration of Gelesis100 over a period of 168 days in overweight and obese subjects with and without type 2 diabetes
- To demonstrate safety and tolerability similar to placebo or clinically acceptable of repeated administration of Gelesis100 over a period of 168 days in overweight and obese subjects with and without type 2 diabetes

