## **15.8 Statistical Methods**

A SAP will be developed and approved before the database is locked. The SAP will present the detailed statistical methodology to be used in analyzing the effectiveness and safety data from this trial.

All the effectiveness endpoints presented here will be conducted using both the ITT and the PP populations. All safety analyses will be conducted using the safety population.

All data collected will be summarized according to the variable type:

- Continuous data summaries will include:
  - Number of observations, mean, SD, median, minimum, and maximum values
  - ANCOVA with the stratification factors and the respective baseline values for the endpoint in the model for inferential statistics
- Categorical data summaries will include:
  - Frequency counts and percentages
  - Logit model with the stratification factors and the respective baseline values for the endpoint in the model for inferential statistics
- Time-dependent data:
  - Cox proportional hazards model will be used to analyze time-dependent data
  - Kaplan-Meier will be used to depict the time to event data

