### **15.8.3 Extent of Exposure to Study Product**

Extent of exposure to the study product will be summarized for each arm.

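### The adverse event tables use no follow-up denominator and no between-arm interval, so they cannot support or refute the objective of safety similar to placebo

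*Combined protocol and SAP*

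**What the plan says.** On adverse events (AEs), section 15.8.7.1 states: "All AEs will be presented by number of episodes and by number of subjects experiencing the event in each arm". The same sentence goes on to promise when events occurred and how long they lasted. The section adds that "TEAEs will be summarized by treatment arm, System Organ Class, and Preferred Term", with breakdowns by severity and relationship, and separate summaries of serious AEs and of AEs leading to discontinuation of treatment. Treatment-emergent AEs (TEAEs) are defined by a start (onset on or after first treatment) but have no end date.

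The objective in section 6.2 is stronger than a description: "To demonstrate safety and tolerability similar to placebo or clinically acceptable". No criterion for either limb is given.

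Other relevant statements:

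- Section 15.8.3: "Extent of exposure to the study product will be summarized for each arm". This is not linked to the AE tables.
- Section 15.8: "Cox proportional hazards model will be used to analyze time-dependent data", and Kaplan-Meier is named for time-to-event data. Neither is assigned to a safety variable.
- Section 13.1.3: AEs are collected until 28 days after the last administration.
- Sections 7 and 12.2.13: subjects who complete 24 weeks and lose at least 3% of body weight may enter an open-label extension. Visit 13 (Day 171) is then their last visit, instead of Visit 14 (Day 197).
- Section 15.4: 30% dropout is assumed, with the same number of completers in each arm.
- Section 5.2.1.2, on the earlier FLOW study: "Dropout after randomization occurred in 2 subjects (5%) on Gelesis100 2.25 g", against 24% on 3.75 g and 21% on placebo.

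**The concern.** There are two separate gaps.

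The first exists whatever the dropout. An objective to demonstrate similarity needs an estimate of the difference between arms and a statement of its precision. Two columns of counts give neither, and a reader would have to judge similarity by eye.

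The second is conditional. A subject followed for longer has more time to report an event. If one arm stays in the study longer, it collects more episodes and more affected subjects at the same underlying rate. The AE tables would show this as a difference in safety, and the separate exposure table does not correct it.

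Unequal follow-up is plausible here. FLOW saw different dropout at this amount and on placebo. Section 14.2.1 ties discontinuation to rises in HbA1c, lipids and blood pressure, which may differ by arm if the product works. Entry to the extension depends on weight loss.

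**Working it through.** **The plan's own figures.** The documents give no number for the AE analysis. The figures that frame it reproduce: 230 × (1 − 0.30) = 161 completers per arm. With 161 per arm, a distance of 4.5 − 3.0 = 1.5 from the margin, SD 5.0 and one-sided alpha 0.05, power is Φ(1.5/(5√(2/161)) − 1.645) = Φ(1.047) = 0.852, matching the stated 85%.

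**Step 1: precision of a between-arm difference.** Take FLOW's rates for any gastrointestinal AE (60% on 2.25 g, 74% on placebo) and 230 per arm.

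Half-width = 1.96 × √[(0.60×0.40 + 0.74×0.26)/230] = 0.085, or about ±8.5 points.

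The same calculation on FLOW itself (25/42 against 32/43) gives −14.9 points, 95% CI −34.7 to +4.9. A point comparison alone says little about similarity.

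**Step 2: episode counts under unequal dropout.** Inputs are 24 weeks of treatment, FLOW dropout of 5% and 21%, and equal true event rates (assumed).

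- Dropout spread evenly, observation ending at dropout: (1 − 0.05/2)/(1 − 0.21/2) = 0.975/0.895 = 1.089.
- Constant dropout hazard, mean weeks = 24d/(−ln(1−d)): 23.39 against 21.38, ratio 1.094.
- Even spread plus 4 weeks of post-dose collection for everyone: (23.40 + 4)/(21.48 + 4) = 1.075.
- Even spread, post-dose collection for dropouts only (all completers leaving at Visit 13): (23.40 + 0.05×4)/(21.48 + 0.21×4) = 1.057.
- Equal dropout: 1.00.

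At a constant event rate, episode counts shift by the same factor.

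**Step 3: affected subjects.** Let L = −ln(1 − p), where p is the true 24-week risk, and H = −ln(1 − d). With constant hazards and observation ending at dropout, the crude proportion is L/(L+H) × (1 − e^−(L+H)).

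| True risk p | Crude, 5% dropout | Crude, 21% dropout | Spurious gap |
|---|---|---|---|
| 10% | 9.8% | 8.9% | 0.8 points |
| 74% | 72.5% | 67.6% | 4.9 points |
| 84% | 82.5% | 77.4% | 5.1 points |

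With 30% dropout in both arms the gap is zero. For scale, the sampling half-width at 230 per arm is 5.5 points at 10% risk and 6.7 points at 84%.

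**Step 4: exit to the extension.** The last dose is on Day 168, so the 28-day collection period runs to Day 196. An extension entrant's last visit is Day 171, which is 197 − 171 = 26 days before Visit 14. If, as an assumption, 60% of completers on active and 40% on placebo enter the extension, observed time per completer is (171 + 26×0.4)/(171 + 26×0.6) = 181.4/186.6 = 0.972. That is about 3% less on active, opposite in direction to Step 2 at the FLOW dropout rates.

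**The case against.** **Timing is not ignored.** The same sentence of section 15.8.7.1 promises time of occurrence and duration, and exposure is summarized by arm. A reader might infer that the plan discards time altogether, but it does not. What stands is narrower: follow-up is not used as a denominator.

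**Methods are deferred to a separate SAP.** Sections 15 and 15.8 say so, and that SAP is not in the supplied text, so it may contain what is missing. The deferral is general, though. Section 15.8.7 states how AEs will be reported and, unlike the sections on missing data, subgroups and longitudinal analyses, does not itself refer the method to the SAP.

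**The objective has a second limb.** Clinically acceptable is a matter of judgement and needs no between-arm interval, and the text says that AEs are presented and summarized, not formally compared. That is correct. The similarity limb remains without an analysis.

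**The distortion is conditional and its direction uncertain.** The plan assumes equal completion. FLOW's contrast is 2 against 9 subjects over 12 weeks (Fisher p about 0.05, taking the safety-population denominators 42 and 43). The 3.75 g arm dropped out slightly more than placebo, and the two active arms together had 12/83 (14%) against 9/43 (21%), p about 0.45. A reader might infer that the bias must run against the product, or for it; the documents support neither. Larger figures can be produced, such as 12.5% from a 20%/40% split or 25% from 11%/49%, but those splits appear nowhere in the documents.

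**Readers can compute the intervals themselves.** For subject proportions, yes. They cannot recover cumulative incidence or a common at-risk window from the planned counts.

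**Conclusion.** The concern holds in two parts of different strength.

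The firm part is that no between-arm difference, interval or criterion is planned, so similarity to placebo cannot be supported or refuted by section 15.8.7.1 as written. This does not depend on dropout.

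The conditional part is that unequal follow-up could distort crude counts. At FLOW's dropout the shift is about 7.5% to 9% in episodes (nearer 6% if all completers leave at Visit 13) and about 1 to 5 points in affected subjects, below the sampling half-width at the risks shown. This rests on equal true rates, event and dropout rates that do not change with time (or evenly spread dropout), and a 12-week dropout pattern carried over to 24 weeks. Early clustering of events would make it smaller. Equal dropout removes it, and higher dropout on active reverses it. Exit at Visit 13 can shift follow-up even when dropout is equal. The net direction cannot be read from the counts, which is the reason to define a denominator.

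**What to change.** In section 15.8.7.1 or the SAP, for any TEAE, gastrointestinal TEAEs, serious AEs and AEs leading to discontinuation:

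1. Define one at-risk window common to both arms, for example first dose to Day 171 or earlier study exit.
2. Report by arm the proportion of subjects affected and the cumulative incidence to Week 24, each with the between-arm difference and 95% CI. Kaplan-Meier serves for most categories. For AEs leading to discontinuation use a competing-risk estimate, because other dropout precludes the event.
3. Add events per subject-time over the same window as a supplement only. A bare rate per week of dosing would count post-dose events without their time and would assume a constant hazard.

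Reword section 6.2 from demonstrate to assess, judged on these intervals. Reconcile the Visit 13 exit in section 12.2.13 with the 28-day AE collection rule in section 13.1.3.

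The cost is a few extra tables; the sample size does not change, and AE onset dates and dosing dates are already recorded. The intervals will be descriptive, since the trial is not powered for safety: about ±8.5 points for any gastrointestinal AE at the FLOW rates.

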Before lunch	$1.71 \pm 1.00$	$1.67 \pm 0.83$	0.702
Before dinner	$1.47 \pm 1.16$	$1.77 \pm 0.98$	0.011

The placebo-adjusted effect of Gelesis100 on hunger (second meal effect) is reported in Figure 3.

**Figure 3.** Placebo-adjusted change in pre-meal hunger scores (%) before lunch and dinner, after Gelesis100 administration before breakfast and lunch, respectively.

Treatment with Gelesis100 was safe and well tolerated. Fifteen subjects (15.8%) reported at least 1 symptom during the study. No detailed information was recorded as to whether the symptoms occurred after the administration of Gelesis100 or placebo (or both). Gastrointestinal symptoms (solicited adverse events “AEs”) were reported in 13 subjects (13.7%) during the study (Table 5).

**Table 5.** Gastrointestinal symptoms during Gelesis100/Placebo administration in 95 subjects.

Symptoms*	Number of subjects	Percentage of subjects
Nausea	7	7.4
Constipation	4	4.2
Stomach ache	4	4.2
Vomiting	1	1.1
Diarrhea	1	1.1

\*No information was recorded as to whether the symptoms occurred after the administration of Gelesis100 or placebo.

Three subjects (3.2%) reported more than 1 gastrointestinal symptom during the study: 2 reported 2 symptoms (stomach ache and diarrhea, nausea and constipation) and 1 reported 3 symptoms (nausea, vomiting, and stomach ache). Of the 7 subjects who

reported nausea during the study, all had a medical history of at least 1 gastrointestinal disorder (esophagitis, epigastralgia, colitis, constipation, and proctitis). Non-gastrointestinal symptoms (isolated headaches) were reported in 2 subjects (2.1%) during the study. No serious AE (SAE) was observed during the study.

In conclusion, a single administration of Gelesis100 significantly increases the post-meal feeling of satiety in humans. The administration of Gelesis100 before lunch significantly decreases the feeling of hunger before the subsequent dinner. The treatment is safe and well tolerated.

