### **13.1.2 Definitions**

An AE is any untoward medical occurrence (sign, symptom, illness, abnormal laboratory value, or other medical event) in a subject, whether or not related to the investigational medical device. This includes events related to the procedures involved (any procedure in the Clinical Investigation Plan).

A SAE is any AE that:

- led to death
- resulted-in a life-threatening condition
- resulted-in a permanent impairment of a body structure or a body function
- required inpatient hospitalization or prolongation of existing hospitalization for  $\geq 24$  h (elective hospitalizations and/or hospitalizations for treatment of pre-existing conditions that did not worsen from baseline are not considered AEs and should not be reported as SAEs)
- resulted-in a medical or surgical intervention to prevent permanent impairment to a body structure or a body function
- led to fetal distress, fetal death or a congenital abnormality, or birth defect

A device deficiency is an inadequacy of the medical device with respect to its identity, quality, durability, and safety (e.g., use errors and inadequate labeling). Medical device

---

deficiency can lead to an adverse device effect (ADE) or a serious ADE (SADE) (see below).

For the purpose of this study and for reporting purposes, all device deficiencies that could have led to SAEs, if suitable action had not been taken or intervention had not been made, or if circumstances had been less fortunate, will also be considered as SAE.

An ADE is an AE with a reasonable causal relationship to the use of the investigational medical device (i.e., an AE assessed as either “most probably related” or “possibly related” to the use of medical device) (see Section 13.1.3).

An unanticipated ADE (UADE) is an ADE not previously reported or an ADE that occurs with specificity, severity, frequency, or outcome that is not consistent with the current Investigator’s Brochure (8).

A SADE is a SAE with a reasonable causal relationship to the use of the investigational medical device (i.e., a SAE assessed as either “most probably related” or “possibly related” to the use of medical device). For Canada, this definition is equivalent to the Canadian definition of an incident.

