### **13.1.3 Adverse Event and Device Deficiency Recording, Assessment, and Reporting Procedure**

All AEs regardless of seriousness or relationship to the investigational medical device including those occurring during the screening period (after the signature of the Informed Consent Form) are to be recorded in the appropriate electronic CRF.

AEs reported by subject will be discussed in details and recorded by the Investigator at each visit. AEs will be collected until 28 days after the last administration of the investigational medical device (i.e., until subject terminates his/her participation in the study).

The Investigator should specify the date of onset, severity, action taken with respect to the investigational medical device, corrective treatment, outcome, and whether or not there is a reasonable possibility that the AE may have been caused by the use of the investigational medical device.

AEs are graded as follows:

- Mild: sign or symptom, usually transient, requiring no special treatment and generally not interfering with usual activities.

---

- Moderate: sign or symptom, which may be ameliorated by simple therapeutic measures, may interfere with usual activity.
- Severe: sign or symptom intense or debilitating and interfering with usual activities without being immediately life-threatening. Recovery is usually aided by therapeutic measures.
- Very severe: sign or symptom life-threatening. Urgent intervention indicated.

The assessment of the relationship of an AE to the use of the medical device is a clinical decision based on all available information at the time of the completion of the electronic CRF:

- Most probably related: follows a reasonable temporal sequence from medical device use, and cannot be reasonably explained by known characteristics of the subject's clinical data.
- Possibly related: follows a reasonable temporal sequence from medical device use, but could have been produced by the subject's clinical state regardless of the medical device.
- Probably not related: temporal association is such that the medical device use is not likely to have had any reasonable association with the observed event.
- Not related: no relationship to the use of the medical device is perceived.

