Abnormalities of vital signs and laboratory results are to be recorded as AEs only if they are considered by the Investigator as clinically significant (symptomatic, requiring corrective treatment, leading to discontinuation, or fulfilling a seriousness criteria).

Any pre-existing conditions or signs and/or symptoms present in a subject prior to the Screening Visit should be recorded as medical/surgical history.

In this study, the following events will be reported to the authorities on expedited basis:

- All SAEs (including SADEs) will be expeditiously reported to the relevant European Regulatory Authorities and the Ethics Committees.
- All newly discovered pregnancies will be expeditiously reported, if required by the local regulations.
- All suspected USADEs will be expeditiously reported to the US Food and Drug Administration (FDA) and the US Institutional Review Boards.
- All incidents occurring in Canada will be expeditiously reported to Health Canada.

All device deficiencies are to be recorded in the appropriate electronic CRF.

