### **13.1.4 Anticipated Adverse Device Effects**

The ADEs anticipated with the administration of Gelesis100 in overweight or obese subjects include nausea, dyspepsia (heartburn), abdominal distension (bloating), flatulence, abdominal pain, diarrhea, defecation urgency, and constipation. These AEs

---

were observed in the FLOW study. A comprehensive list of anticipated ADEs is provided in the Investigator's Brochure (8).

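### The treatment-emergent definition has no worsening clause and sites are not told how to record worsening, so a gastrointestinal complaint that worsens on product may be missed by the TEAE tables

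*Combined protocol and SAP*

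**What the plan says.** Section 15.8.7.1 sets the rule by date of onset alone: "Treatment-emergent AEs (TEAEs) are defined as events with an onset on or after the first randomized treatment". The tables by System Organ Class and Preferred Term, by severity grade and by relationship are all TEAE tables.

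Section 13.1.3 governs what sites record. For complaints that predate screening: "Any pre-existing conditions or signs and/or symptoms present in a subject prior to the Screening Visit should be recorded as medical/surgical history". Adverse events of any kind, "including those occurring during the screening period (after the signature of the Informed Consent Form) are to be recorded in the appropriate electronic CRF", so a complaint that starts in screening is an adverse event with an onset before the first dose. The section asks for onset date and severity, but does not say whether a later rise in severity opens a new record.

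Worsening appears once in the adverse event rules, inside the hospitalization criterion of section 13.1.2: "hospitalizations for treatment of pre-existing conditions that did not worsen from baseline are not considered AEs". This implies that a worsened condition can be an adverse event, but no general rule follows from it.

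Section 15.8.7.1 also has outputs that are not limited to TEAEs. One is a general presentation: "All AEs will be presented by number of episodes and by number of subjects experiencing the event in each arm". The others are separate summaries of serious events and of events leading to discontinuation of treatment.

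**The concern.** The device effects that section 13.1.4 anticipates are "nausea, dyspepsia (heartburn), abdominal distension (bloating), flatulence, abdominal pain, diarrhea, defecation urgency, and constipation". Several of these can already be present at entry. Section 8.4 excludes reflux disease, ulcer, gastroparesis (described there by chronic nausea, vomiting and heartburn), malabsorption and laxative users, among others. It does not name bloating, flatulence, abdominal pain, diarrhea, defecation urgency, or constipation managed without laxatives.

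For such a subject the likely sign of intolerance is an existing complaint getting worse. If that has no defined place in the TEAE tables, the main tables of tolerability describe new complaints only, plus whatever worsening individual sites chose to enter as new events. With approximately 38 sites (section 8.2), consistent handling cannot be assumed without an instruction. The secondary objective in section 6.2 is tolerability similar to placebo or clinically acceptable, so the between-arm comparison in these tables is what readers will use.

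**Working it through.** The plan attaches no figure to this definition, so there is nothing to reproduce. The check has two parts.

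**1. Following one complaint through the rules**

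| Situation | Record | Onset relative to first dose | TEAE tables | Other outputs |
|---|---|---|---|---|
| New after first dose | Adverse event | After | Yes | All-AE presentation |
| Present before screening, worsens; site leaves it in history | Medical history only | Not applicable | No | None |
| Starts in screening, worsens; site keeps one record | Adverse event | Before | No | All-AE presentation |
| Either of the last two, entered by the site as a new event | Adverse event | After | Yes | All-AE presentation |

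A worsening recorded as an adverse event that is serious or leads to discontinuation also reaches those summaries. The last three rows can describe the same clinical course. Which one applies depends on the site's choice, and sections 13.1.2 and 13.1.3 do not settle it.

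**2. What the omission can do to the difference between arms**

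Let q be the share of subjects with the complaint at first dose, r1 and r0 the new-onset risks (active, placebo) in those without it, and w1 and w0 the worsening risks in those with it.

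- Onset-only difference = (1 − q)(r1 − r0)
- Difference with worsening counted = (1 − q)(r1 − r0) + q(w1 − w0)
- Omitted term = q(w1 − w0)

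The omitted term takes its sign from w1 − w0 alone. If sites enter a fraction e of worsenings as new events, equally in both arms, it becomes (1 − e) × q(w1 − w0).

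All rates below are assumptions, because the documents give none: r1 = 30%, r0 = 20%, e = 0. Entries are percentage points, active minus placebo.

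| q | Onset-only | w1 = 30%, w0 = 20% | w1 = 50%, w0 = 20% | w1 = w0 = 20% | w1 = 20%, w0 = 30% |
|---|---|---|---|---|---|
| 5% | 9.5 | 10.0 | 11.0 | 9.5 | 9.0 |
| 10% | 9.0 | 10.0 | 12.0 | 9.0 | 8.0 |
| 20% | 8.0 | 10.0 | 14.0 | 8.0 | 6.0 |
| 30% | 7.0 | 10.0 | 16.0 | 7.0 | 4.0 |

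Example at q = 10%, w1 = 50%, w0 = 20%: onset-only 0.90 × 10 = 9.0; omitted 0.10 × 30 = 3.0; total 12.0. The onset-only rule then keeps 9.0/12.0 = 75% of the difference. With 230 subjects per arm (section 15.5.1), the subjects with uncounted worsening would number 230 × 0.10 × 0.50 = 11.5 on active and 230 × 0.10 × 0.20 = 4.6 on placebo.

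**The case against.** The strongest reply is that the plan is silent on worsening but does not exclude it. Section 13.1.2 defines an adverse event broadly, its hospitalization clause exempts only conditions that did not worsen, and nothing forbids entering a worsening as a new event. Such an entry has an on-treatment onset and is a TEAE under the present wording. The general presentation and the summaries of serious events and discontinuations are not limited to TEAEs. Some worsening would also surface through sections 9.2.1 and 14.2.1, where the need for a prohibited medication, including one affecting gastrointestinal motility, is a reason to discontinue. All of this stands, and it means that loss is possible but not certain.

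A reader might go further and infer that the rule makes Gelesis100 look closer to placebo than it is. The documents do not support that. The active-minus-placebo difference is understated only if worsening is more frequent on active. In FLOW (section 5.2.1.2, Table 10) any gastrointestinal event was reported by 25/42 (60%) on 2.25 g and 32/43 (74%) on placebo, so an excess on active cannot be presumed. If worsening followed that pattern, the omission would hide an advantage of the product.

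The satiety study (section 5.2.1.1) is also tempting evidence, since the 7 subjects with nausea "all had a medical history of at least 1 gastrointestinal disorder". The disorders listed there do not include nausea, and the study did not record whether symptoms followed active or placebo. New nausea in someone with a history of constipation has a new onset and would count. The study shows that people with a gastrointestinal history can enter such research, not that existing complaints worsened.

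Finally, sections 15 and 15.8 leave detailed conventions to a separate SAP that is not among the documents, and it might add a worsening clause. That helps only in part. Section 15.8.7.1 already states the definition, and a SAP that need only be approved before database lock cannot recover worsening that sites never recorded.

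**Conclusion.** The gap is real and worth closing. The TEAE definition depends on onset alone, and no section tells sites to record worsening as a new event. Whether a worsened complaint enters the tables by class, severity and relationship therefore depends on site practice. The general presentation is only a partial backstop: it shows what was recorded, and the plan does not say that it will be broken down by severity or relationship.

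The resulting distortion can go either way: the active-minus-placebo difference is understated if worsening is more frequent on active, unchanged if equal, and overstated if more frequent on placebo. Across the assumed rates it runs from none to 9.0 points too low (7.0 against 16.0) or 3.0 points too high (7.0 against 4.0). Those figures rest entirely on assumed prevalence and risks and on no worsening being entered as a new event. The effect is confined to descriptive tables, since the plan gives no margin or test for tolerability. No effectiveness result is touched.

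**What to change.** In section 15.8.7.1, define a TEAE as an event with onset on or after first study product intake, or one present before it that increases in severity or becomes serious afterwards.

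In section 13.1.3, require such worsening, whether of a medical-history condition or of a screening-period event, to be recorded as a new adverse event with its own date and severity grade. This instruction has to reach the sites, because analysis rules cannot supply records that were never made.

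The cost is two sentences and a CRF completion note, which should say that worsening is judged against the state before first intake. Reported TEAE rates would rise somewhat in both arms.
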